5.3.3 Reasons for Withdrawal

Subjects will be informed that they have the right to withdraw from the study at any time for any reason without prejudice to their medical care. Data collected for withdrawn subjects will be evaluated for safety and PK.

Subjects may be withdrawn from the study for any of the following reasons:

1. Withdraws consent;
2. Noncompliance with study procedures and/or requirements;
3. Death;
4. Pregnancy;
5. In the opinion of the site PI and Sponsor, does not meet eligibility criteria upon admission to unit;
6. Has met Halting Criteria (see [Section 9.7](#))
7. Administrative reasons/other.

In all cases of withdrawal, the reason for withdrawal will be recorded. Subjects who are withdrawn from the study will be asked to complete all Day 15 ± 1 safety assessments including follow-up of any AEs prior to termination from the study. Once randomized, subjects who withdraw from the study for any reason will not be replaced.

5.3.4 Blinding Procedures

Study subjects, the PI and study site personnel will remain blinded to all randomization assignments throughout the study. The Emergent medical monitor and personnel, [REDACTED] DMID medical monitor and NIAID personnel who are in regular contact with the study site and/or involved with documentation associated with the study will remain blinded to all subject randomization assignments. The PK analyst will be provided with dummy subject codes and remain blinded.

Selected individuals not involved in the conduct of the study (i.e. unblinded clinical monitor), including members of the SMC may have access to unblinded data as needed for safety review or other data review.

Pharmacist will remain unblinded during the course of the study.

5.3.5 Emergency Unblinding

Emergency unblinding of treatment assignment for a subject may be necessary due to a medical emergency, or any other significant medical event. Should an SAE or other circumstance require the blind to be broken to ensure a subject's safety, the PI should immediately notify Emergent (within 24 hours) to discuss the case and reason for unblinding (a written narrative must follow within 48 hours of the event).

Emergent Medical Monitor:

If emergency unblinding is required for a medical emergency:

1. The PI will make the decision to unblind the treatment assignment for AE's involving individual subjects;
2. An unblinding memo with the specific details for breaking the blind, including the rationale for unblinding and specific information regarding the subjects that are to be unblinded will be prepared by the site coordinator;
3. The document will be sent out for approval and signature to the PI, Emergent Medical Monitor and/or Sponsor Representative, as appropriate;
4. The original signed memo will be kept in the investigator site file and a copy of the signed document will be sent to the Sponsor;
5. The Site coordinator or designee will send the signed copy of the unblinding memo to the [REDACTED] unblinded pharmacist, who will send the randomization treatment to the PI (utilizing code break envelopes);
6. The PI will review the unblinding information, and, and continue to monitor/treat the subject as medically appropriate;
7. The [REDACTED] Clinical Project Manager will notify the study team that unblinding has occurred and will provide a copy of the unblinding memo as appropriate;
8. The Site Coordinator will notify the Institutional Review Board (IRB) that a request has been sent to the pharmacist to unblind the treatment assignment of a subject. Once available, the results of the unblind will be communicated to the IRB.

The treatment assignment is not to be provided to site personnel, including the PI at any time during the conduct of the study, except in the case of an emergency.

Procedures 2 through 8 listed above will be followed should a request come from the FDA to unblind a subject's treatment.

Any information regarding a subject being unblinded will be documented in the subject's study records. If the pharmacist is not on site, the code break envelopes will be available to the PI in case of emergency.

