9.1.7 Evaluation of Hypersensitivity Reactions

Examples of hypersensitivity (HS) reactions include erythema of oropharyngeal and conjunctival membranes, rhinitis, coryza, breathing difficulties including wheezing, dyspnea and stridor, and dermatologic findings to include diffuse pruritus, macular rashes and or vesiculation. Laboratory abnormalities suggestive of HS reaction (e.g., peripheral eosinophilia) require clinical corroboration.

Any evidence of HS reaction during study requires cessation of dosing pending physician evaluation and clinical corroboration. If HS reaction follows dosing, AE or SAE will be

recorded in accordance with physical monitoring criteria or laboratory abnormalities noted in [Appendix II](#).

The Phase 1 treatment facility is capable of managing all types of HS reactions from HS type I-IV (e.g., with bedside epinephrine, diphenhydramine, terbutaline and albuterol nebulizers and oral and/or systemic steroids). [REDACTED] will follow their Standard Operating Procedures (SOPs) for treatment of HS reactions. Please see general anaphylaxis protocol ([Appendix V](#)).

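### With the pharmacist on site, the emergency unblinding steps put a signed memo before release of the code and set no time limit on it

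*Protocol*

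**What the plan says.** Protocol section 5.3.5 introduces eight numbered steps with "If emergency unblinding is required for a medical emergency". The ones that matter here are:

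- Step 1: "The PI will make the decision to unblind the treatment assignment for" AEs in individual subjects.
- Step 2: the site coordinator prepares an unblinding memo with the details and the rationale.
- Step 3: "The document will be sent out for approval and signature to the PI, Emergent Medical Monitor and/or Sponsor Representative, as appropriate".
- Step 5: "The Site coordinator or designee will send the signed copy of the unblinding memo to the" unblinded pharmacist, who then sends the assignment to the PI from the code break envelopes.
- Step 6: the PI reviews what was released and goes on treating the subject.

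The section has two time limits. The sponsor is to be notified within 24 hours, and "a written narrative must follow within 48 hours of the event".

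Two further sentences bear on the point. The first gives the steps a second use: "Procedures 2 through 8 listed above will be followed should a request come from the FDA to unblind" a subject. The second gives the PI direct access in one situation: "If the pharmacist is not on site, the code break envelopes will be available to the PI in case of emergency". A general sentence bars giving the assignment to site staff, the PI included, except in an emergency.

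**The concern.** Step 5 makes a signed document the trigger for release of the code. A signed copy cannot be sent until the memo has been written and signed, and no sentence allows the memo to follow release. Where the pharmacist is absent, the PI has the envelopes and no memo condition is stated. Followed literally, the PI's access in an emergency is therefore conditional on paperwork when the unblinded person is in the building and unconditional when that person is away. That is unlikely to be intended, and the documents give no reason for it.

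Step 3 adds an uncertainty. It names the PI and two sponsor-side signatories joined by an and/or, to be used as appropriate, so staff would have to decide during the emergency whether the PI's signature alone is enough.

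At stake is the time to a treatment decision in a healthy volunteer, in those emergencies where the decision turns on the assignment. Dosing is every 8 hours for 7 residential days, so an emergency could arise at any hour. The protocol does not say whether the coordinator or a sponsor signatory would be reachable then. Staff who released first and documented afterwards would depart from the written steps, and Protocol section 15.6 treats any noncompliance with the protocol as a deviation that calls for corrective action.

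**Working it through.** No arithmetic beyond counting applies. The three situations in section 5.3.5 can be set side by side.

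| | Emergency, pharmacist on site | Emergency, pharmacist off site | FDA request |
|---|---|---|---|
| Who starts it | PI (step 1) | PI | FDA |
| Memo drafted before release | Yes (step 2) | Not stated | Yes (step 2) |
| Memo signed before release | Yes (step 3) | Not stated | Yes (step 3) |
| Signed copy sent to pharmacist before release | Yes (step 5) | Not stated | Yes (step 5) |
| Time limit on these actions | None | Does not arise | None |

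**Order.** The conclusion does not rest on step numbers. Step 5 itself requires a signed copy to reach the pharmacist, who then releases the assignment. Drafting and signing must come before that.

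**Count, on site.** Draft (step 2) + signature or signatures (step 3) + sending the signed copy (first half of step 5) = 3 actions before release. Step 4 is filing and copying to the sponsor and is not counted.

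**Deadlines.** The 24-hour limit is for notifying the sponsor and the 48-hour limit is for the narrative. Neither names the memo, its signature or the release, so 0 of the 3 actions have a time limit.

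**Count, off site.** 0 memo actions are stated before the PI reaches the envelopes.

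**No expedited path on site.** The FDA-request route uses steps 2 to 8, so the on-site emergency passes through the same 3 actions as a request that need not be urgent.

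**Other sections.** I looked for another emergency route or a release deadline in Protocol sections 5.3.1 (randomization), 5.3.4 (blinding), 9.2.2 and 9.3.1 (SAEs) and 9.8.2 (SMC), and in SAP section 11. There is none.

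**What does not need the code.** For suspected hypersensitivity, section 9.1.7 says "Any evidence of HS reaction during study requires cessation of dosing pending physician evaluation and clinical corroboration". Section 9.2.2 pauses dosing for any SAE. Section 9.7 stops dosing in a subject with a Grade 3 event or frank bleeding. Appendix V treats anaphylaxis. None of these uses the assignment.

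**The case against.** The strongest reply is that this is a drafting gap with little clinical consequence.

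- The PI holds the decision, and notice to the sponsor is not a request for permission. Step 3 can be read as met by the PI's own signature, in which case the on-site barrier is a short memo signed at the same unit.
- The emergency exception permits disclosure to the PI. The envelope sentence reads naturally as a safeguard against the pharmacist's absence, not as a bar on prompt release when the pharmacist is present.
- The list is not strictly chronological. Step 8 tells the IRB that a request has gone to the pharmacist, yet it stands after the step in which the PI reviews the result.
- Dose is fixed by cohort and 6 of 8 subjects receive active drug, so a clinician can assume active drug. No visible text describes care that differs by assignment, and the risk section is redacted.
- The Pharmacy Manual may hold a faster procedure.
- A count of actions is not a measure of delay.

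Much of this stands as a limit on the harm. The text is not a clear sponsor veto, the delay could be short, the count measures neither time nor risk, and the documents name no scenario in which the code would change care.

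It does not remove the rule. The exception permits disclosure but gives no route, and the only on-site route described runs through the signed memo. Loose ordering elsewhere in the list does not alter the wording inside step 5. Section 5.3.1 refers to the Pharmacy Manual for randomization details, whereas section 5.3.5 refers to no other document for unblinding. Cases where the code is not needed are also not the ones this section is written for.

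**Conclusion.** The concern holds. With the pharmacist on site, section 5.3.5 places 3 memo actions between the PI's decision and release of the code. None has a time limit, and there is no faster path than the one used for an FDA request. With the pharmacist off site, no memo action is stated before access.

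The delay cannot be put in minutes or hours from these documents. It could be short if the PI's signature is enough, and longer if a sponsor signature is needed. The conclusion assumes that staff follow the steps as written and that no site procedure or Pharmacy Manual text outside the documents supplies a quicker route. The effect is confined to emergencies in which the PI judges that the assignment would change care. No endpoint or analysis depends on it. The section should be corrected because it states a rule that serves the subject worse when followed literally.

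**What to change.** Amend section 5.3.5 as follows.

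1. State that in any medical emergency the PI may obtain the assignment at once, from the unblinded pharmacist or by opening the code break envelope, whether or not the pharmacist is on site.
2. Make the memo and its signature documentation that follows release, with its own deadline. It could fall due together with the 48-hour narrative.
3. Say whose signature is required.
4. Keep sponsor notification within 24 hours.
5. Keep the signed-memo-first sequence for FDA-requested, non-emergency unblinding.

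The cost is a re-ordering of steps and about two added sentences in one section. Release remains limited to documented emergencies, and only the timing of the documentation changes.

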5.3.6 Termination of Study

Emergent, DMID, and the FDA may terminate the study in the interest of subject safety and welfare. In addition, DMID reserves the right to terminate the study at any time for any other

reason. If DMID terminates the study, the PI, IRB, SMC, Emergent, and the FDA will be informed, activities will be closed, and a study report will be prepared.

6 STUDY INVESTIGATIONAL PRODUCT

6.1 Study Product Description

6.1.1 Acquisition

Study product will be shipped to the clinic upon request by Emergent.

Sterile water for irrigation and OraSweet-SF will be obtained by the Pharmacy ([section 6.1.2.2](#)).

6.1.2 Formulation, Packaging, and Labeling

6.1.2.1 UV-4B

UV-4B for solubilization for the Phase 1b clinical program is manufactured, packaged, labeled, and released by [REDACTED]

Clinical trial material is UV-4B drug substance, packaged in double bags in containers in a configuration supported by previous and ongoing UV-4B stability programs. [REDACTED]

6.1.2.2 Sterile Water for Irrigation (WFI)

Sterile Water for Irrigation, USP is sterile, distilled, nonpyrogenic water for injection intended only for sterile irrigation, washing, rinsing, and dilution purposes. It contains no bacteriostat, antimicrobial agent or added buffer and is supplied only in single-dose containers. WFI will be used to solubilize the UV-4B drug substance, for intermediate UV-4B dilutions, and for placebo preparation.

6.1.2.3 OraSweet-SF

Commercially available OraSweet-SF contains purified water, glycerin, sorbitol, sodium saccharin, xanthum gum, and flavoring. It is buffered with citric acid and sodium citrate and contains methylparaben, potassium sorbate, and propylparaben as preservatives. OraSweet-SF will be used as a taste-masking agent. Use of OraSweet SF ensures the active and placebo dose solutions match in appearance, taste, and consistency. Masking procedures are described in [Section 5.3.2](#).

6.1.3 Product Storage and Stability

6.1.3.1 UV-4B

For the study, containers of UV-4B will be shipped and stored under 2-8°C refrigerated conditions under locked and limited access.

6.1.3.2 Sterile Water for Irrigation (WFI)

Store according to manufacturer specifications at 20-25°C (68°F to 77°F) [See USP Controlled Room Temperature; excursions between 15°C and 30°C (59°C and 86°F) are permitted]. Protect from freezing.

6.1.3.3 OraSweet-SF

OraSweet-SF will be stored according to manufacturer specifications.

6.2 Dosage, Preparation, and Administration of Study Investigational Product

6.2.1 Dosage and Administration

UV-4B or Placebo will be administered orally as a 30mL oral solution TID for 7 days (every 8 hours \pm 0.5 hours). A 50 mL rinse of the dosing container with tap water and an additional 160 mL of tap water will immediately follow each dose.

Details regarding planned dosing are included in [Section 2.2](#) and in the Pharmacy Manual

6.2.2 UV-4B Preparation

At time of use, bulk drug substance will be removed from the container and weighed in the clinic pharmacy. An amount appropriate to the number of subjects being dosed and the dose to be administered will be solubilized in WFI. Gentle mixing by inversion will be used to solubilize the drug substance and generate a UV-4B stock solution. If required or convenient for the preparation of dilute dosing solutions, an intermediate dilution stock solution in WFI may be made. An appropriate volume of UV-4B stock solution will be removed using a syringe, and transferred into an oral dosing container. 10 mL of taste-masking agent (commercially obtained OraSweet-SF) will be added. If required, additional WFI will be added to increase the volume to 30 mL. The WFI and any glassware or plastic ware used for solubilization of the UV-4B and dilution and dosing of the drug substance will be sourced by the [REDACTED] Phase 1 unit. Detailed dose preparation instructions will be provided in the pharmacy manual.

6.2.3 Placebo Preparation

Placebo will be 10 mL of taste masking agent diluted to 30 mL with WFI. Detailed dose preparation instructions will be provided in the pharmacy manual.

Consumption of water will be restricted, other than what is required for study product dilution and rinsing, for one hour prior to dosing and for 1 hour post dosing.

The dates and times of UV-4B administration will be recorded in the subjects' electronic Case Report Form (eCRF).

6.3 Accountability Procedures for the Study Investigational Product

The Research Pharmacist (or designee) will keep a record of the dates and amounts of study product received (including packing slips), the amount dispensed to study subjects, any amount destroyed, and the amount unused. Product accountability will be recorded by the Research Pharmacist on a Product Disposition Record or equivalent document with a separate accountability record for study product and placebo. Upon completion of product accountability, all unused study product will be returned or destroyed per Emergent requirements and instructions once the relevant accountability records and monitoring visit report have been submitted to Emergent.

6.4 Assessment of Subject Compliance with Study Investigational Product

Study product is administered to the study subjects during the in-clinic phase by appropriately trained and designated clinic personnel. Dose administration information such as date/time, complete, or incomplete dosing will be documented in the source documentation and in the eCRF for each subject by the study personnel (see [Section 7.3.1](#)).

All subjects will be administered the assigned study product or placebo TID (every 8 hours \pm 0.5) for 7 days. The total volume of each dose of the study product solution plus the rinse(s) and water will be 240 mL.

The following procedures will be instituted in cases of incomplete or interrupted dosing of subjects:

- In the event of partial dosing, either due to dosing error, or the subject coughing, gagging or spilling solution, the subject will only be followed for safety measurements as defined in [Section 5.3.3](#). PK samples will not be taken.

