7.3 Treatment Period

The specific order of evaluations conducted during the treatment period will be defined by the [REDACTED] Biometrics system.

7.3.1 Day 1

Prior to the administration of the first dose of study product, the following procedures will be performed:

- Brief physical examination focused on the examination of skin and oropharyngeal mucosa for evidence of bleeding and/or bruising (oral [gums] and evidence of hematoma, ecchymosis or petechia), brief neurological examination (mental status, motor system, and sensory system);
- Confirm that subject adhered to fasting requirements of at least 3 hours before the first dosing;
- Obtain vital signs (blood pressure, pulse rate, after being supine for 10 minutes, and orthostatic blood pressure and pulse rate (taken after 2 minutes in the standing position), respiratory rate and oral temperature;
- Obtain a triplicate 12-lead ECG;
- Obtain baseline blood sample for PK analysis ($t=0$), to be taken within 1 hour prior to first dose;
- Telemetry starting at -0.5 hours on Day 1 through at least 4 hours post the first dose;
- Randomization

All subjects will be administered the assigned study product or placebo. The total volume of each dose of the study product solution plus the rinse(s) and water will be 240 mL.

- The following procedures will be instituted to reduce incomplete or interrupted dosing of subjects:
In the event of partial dosing, either due to dosing error, or the subject coughing, gagging or spilling solution, the subject will only be followed for safety measurements as defined in [Section 5.3.3](#).

Following the administration of study product, the following procedures will be performed:

All physical exams, blood tests and ECGs after subjects have been dosed are obtained at approximately the same time each morning (within 2 hours).

- Obtain clinical chemistry, hematology, and coagulation;
- Obtain blood samples for PK analysis at 0.25 (± 5 min), 0.5 (± 5 min), 1 (± 10 min), 1.5 (± 10 min), 2 (± 10 min), 2.5 (± 15 min), 3 (± 15 min), 5 (± 30 min), 6 (± 30 min), 8 (± 30 min) hours (8 hour sample to be collected immediately before the second dose).
- Obtain vital signs (blood pressure and pulse rate including oral temperature and respiratory rate) at 1, 2, 3, 4, 5, 6 and 7 hours (± 15 minutes), after each administration of the study product. Vital signs should be taken after being supine for 10 minutes,

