7.3.2 Day 2 through Day 7 (In-Clinic)

All subjects will be administered the assigned study product or placebo according to the dosing schedule. If a subject has a missed or incomplete dose as described above ([Section 7.3.1](#)) the subject will continue to the next dose as planned. Subjects will not be allowed to miss more than four (4) doses after achieving predicted steady state (i.e. after the third dose on day 1) while participating in the study. If a subject misses four (4) or less doses their continued participation in the study will be determined by the PI and the Emergent and NIAID medical monitors on a case by case basis.

As per Section 7.3.1, all physical exams, blood tests and ECGs after subjects have been dosed are obtained at approximately the same time each morning after dosing (within 2 hours).

- Brief physical examination focused on the examination of skin and oropharyngeal mucosa for evidence of bleeding and/or bruising (oral [gums] and cutaneous); symptom directed/targeted examination based on subject symptoms and brief neurological examination (mental status, motor system, and sensory system);
- Obtain vital signs (blood pressure, pulse rate), after being supine for 10 minutes, and orthostatic blood pressure and pulse rate (taken after 2 minutes in the standing position), respiratory rate and oral temperature;
- Obtain clinical chemistry, hematology, coagulation, and urinalysis;

- Obtain fecal occult blood assessment on every stool sample or less frequent as per discretion of the PI. Stool volume and frequency will be recorded;
- Obtain occult blood on all vomitus
- Obtain 12-lead ECG at same time each day (within 2 hours); telemetry starting 0.5 hours prior to the third (3rd) dose on Day 7 continuously through 4 hours post dose;
- Obtain blood samples for PK analysis Days 2-6: one trough sample daily within fifteen (15) minutes before the first dose approximately the same time each day (± 10 min);
- Obtain blood samples on Day 7: immediately (within fifteen minutes) before the final dose, and at 0.25 (± 5 min), 0.5 (± 5 min), 1 (± 10 min), 1.5 (± 10 min), 2 (± 10 min), 2.5 (± 15 min), 3 (± 15 min), 5 (± 30 min), 6 (± 30 min), 8 (± 30 min), 10 (± 30 min), 12 (± 30 min), and 14 (± 30 min) hours after the final dose;
- Review concomitant medication usage;

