7.3.4 Day 10 ± 1 (Outpatient Visit)

The following procedures will be performed:

- Abbreviated physical examination (general appearance, heart, lungs, skin, and abdomen) and brief neurological examination (mental status, motor system, and sensory system). Also perform brief physical examination focused on the examination of skin and oropharyngeal mucosa for evidence of bleeding and/or bruising (oral [gums] and cutaneous);
- Obtain vital signs (blood pressure, pulse rate, after being supine for 10 minutes, respiratory rate and oral temperature);
- Obtain clinical chemistry, hematology, coagulation, and urinalysis;
- Obtain 12-lead ECG;
- Obtain blood sample for PK analysis. Note: this is an optional sample, if warranted by the PK results from earlier cohort or cohorts;
- Review concomitant medication usage;
- Complete AE assessment (including SAEs) which will be recorded on AE source forms throughout the study and placed in the subject's clinic records. Data from the AE source form will be entered in the EDC system. All AEs will be monitored until they are resolved or determined by the site PI to be medically stable;
- Provide instructions to return on Day 15±1.

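### Protocol 6.4 bars PK sampling after a partial dose with no time limit, which conflicts with 7.3.2, where dosing and the later PK draws continue

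*Protocol*

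**What the plan says.** **Protocol 6.4** gives the rule: "In the event of partial dosing, either due to dosing error, or the subject coughing, gagging or spilling solution, the subject will only be followed". That follow-up is restricted to safety, with a pointer to Section 5.3.3, and the rule ends with "PK samples will not be taken". No dose interval, day or end point is stated.

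**Protocol 7.3.1** repeats the rule and the pointer ("the subject will only be followed for safety measurements as defined in" Section 5.3.3) but omits the sentence on PK samples.

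**Protocol 5.3.3** is the section on reasons for withdrawal. The only safety assessments it names are for subjects who have left: "Subjects who are withdrawn from the study will be asked to complete all Day 15" assessments. It also says that withdrawn subjects' data are evaluated for safety and PK, and that randomized subjects are not replaced.

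**Protocol 7.3.2** says that after a missed or incomplete dose "the subject will continue to the next dose as planned". It then orders one trough a day on Days 2-6 and the Day 7 profile ("Obtain blood samples on Day 7: immediately (within fifteen minutes) before the final dose", followed by 13 post-dose times). Neither order has an exception for an earlier partial dose. The Appendix IV footnotes and the sampling table in SAP Section 6 have none either.

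**Protocol 11.4.1 and SAP Section 9** deal with the analysis. PK data from the affected treatment period are excluded after a significant deviation, and inaccurate dosing on the day of PK sampling is a listed example. Neither document defines the affected treatment period.

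**The concern.** Two operative instructions disagree. One stops PK sampling after a partial dose without saying for how long. The other keeps the subject on study drug and orders every later sample. The pointer does not settle it, because it leads to a withdrawal rule that does not fit a subject who is still being dosed.

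A site that applies 6.4 literally would not draw the Day 7 profile in a subject who spilled part of one dose days earlier, and samples not drawn cannot be recovered. Under SAP 10.5.1 that profile supplies the Day 7 AUCs, CL/F, Vz/F, half-life and the numerator of the accumulation ratio. Under SAP 10.6.3 it supplies all the dose-proportionality data. Each cohort has six active subjects. What is at stake is the secondary PK objective and the PK part of the SMC and FDA reviews between cohorts.

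**Working it through.** **1. The plan's own sample count.** From 7.3.1, 7.3.2 and 7.3.4: Day 1, 1 + 10; Days 2-6, 5 troughs; Day 7 into Day 8, 1 + 13; Day 10, 1 ("this is an optional sample, if warranted by the PK results from earlier cohort or cohorts"). Total 11 + 5 + 14 + 1 = 31, and 31 × 3 mL = 93 mL. Both match Table 6. The samples that feed SAP 10.5.1 parameters are 11 + 14 = 25.

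**2. Parameter-feeding samples lost after one partial dose.** There are 3 × 7 = 21 doses. Doses 19, 20 and 21 fall on Day 7, and the profile follows dose 21.

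| Partial dose | No time limit | Affected interval only |
|---|---|---|
| 1 | 10 + 14 = 24 | 10 |
| 2-19 | 14 | 0 |
| 20 | 14 | 1 (pre-final-dose) |
| 21 | 13 | 13 |

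**3. Would the Day 7 profile be usable if drawn?** Full doses between partial dose n and dose 21 number 20 − n. Section 7.3.2 predicts steady state after three doses.

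- Doses 2-17: 20 − n ≥ 3, so the profile should be usable on the protocol's own prediction.
- Dose 18: a Day 6 dose with 20 − 18 = 2 full doses after it, and correct dosing throughout Day 7. Probably usable.
- Doses 19-20: inaccurate dosing on Day 7 itself, so the profile fits a listed exclusion example whether or not blood is drawn.
- Dose 21: the same loss under either reading.
- Dose 1: an interval limit keeps the 14 Day 7 samples. The Day 1 post-dose samples are gone under either reading, and with them the accumulation-ratio denominator. The PK population also requires completed scheduled post-dose measurements, so membership is open.

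**4. Parameters lost.** For a partial dose 2-20 under the unlimited reading, the subject has no value for 6 of the 9 SAP parameters: AUC(0-last), AUC(0-24), CL/F, Vz/F, half-life and accumulation ratio. Cmax, tmax and AUC(0-8) survive for Day 1 only.

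**5. Precision cost of one lost Day 7 profile.** Take cohorts 1-3 at 6/6/6 and the residual SD s unchanged. Slope 90% CI half-width = t(0.95, N−2) × s / √Sxx, with x = ln 30, ln 75, ln 150 = 3.401, 4.317, 5.011. The SD cancels in the ratio to 6/6/6 (N = 18, Sxx = 7.821, t = 1.746). With N = 17, t = 1.753:

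- Loss at 30 mg: Sxx = 7.070; ratio (1.753/1.746) × √(7.821/7.070) = 1.056.
- Loss at 75 mg: Sxx = 7.815; ratio 1.004.
- Loss at 150 mg: Sxx = 7.197; ratio 1.047.

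Cohort log-mean 90% CI: [t(0.95,4)/√5] / [t(0.95,5)/√6] = 0.953/0.823 = 1.159.

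**6. Estimability.** SAP 10.6.3 needs 3 values per dose. With six active subjects, that fails only if four lose the profile.

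**7. Frequency.** The documents give no partial-dose rate. Purely as an assumption, with independent doses at rate p, the chance of at least one partial dose among the 16 doses numbered 2-17 is 1 − (1 − p)^16: 7.7% at p = 0.5%, 14.9% at 1%, 27.6% at 2% and 56.0% at 5%. These figures matter only if a site takes the unlimited reading, and the verdict does not rest on them.

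**The case against.** The strongest reply is that the harmful reading is the less likely one. Staff work from the visit sections and Appendix IV. These order the samples and do not carry the ban, and 7.3.2 mentions the incomplete dose, continues dosing and then lists the draws. Even 5.3.3 says that withdrawn subjects' data are evaluated for PK. Partial doses should also be uncommon: subjects must manage a full sham dose on Day -1 to enrol, and trained clinic staff give every dose. All of this stands, and it keeps the point small. It does not remove the conflict, because 6.4 is a current instruction and nothing says when sampling resumes.

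A second reply is that the analysis rules already confine the damage to the affected data. That holds only in part. Those rules act after collection and do not tell a site whether to draw blood. Their key term is also undefined, and Section 7.3 uses the heading Treatment Period for all the dosing days. Read that way, a subject's whole PK dataset could be excluded, so clarifying 6.4 alone might not bring the saved samples into the summaries.

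A reader might infer that settling 6.4 would rescue the Day 7 profile after a partial dose anywhere in doses 1-20. The documents do not support that: doses 19 and 20 meet a listed exclusion example, and dose 1 leaves PK-population membership open. A reader might also infer that such a subject leaves the study or loses in-clinic safety follow-up because the pointer leads to 5.3.3. Section 7.3.2 rules out automatic withdrawal, since dosing continues; its case-by-case decision concerns participation after missed doses, not PK sampling.

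**Conclusion.** The conflict between 6.4 and 7.3.2 is real, and it is minor. If 6.4 is applied without a time limit, one partial dose needlessly costs a usable Day 7 profile for doses 2-17, and probably 18. The judgement on usability rests on the protocol's prediction of steady state after three doses.

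Per lost profile, the 90% CI of the slope widens by 0.4-5.6% and that of the cohort log mean by about 16%, assuming full cohorts of six and an unchanged residual SD. One loss does not threaten the dose-proportionality analysis, and the SAP already advises caution because the study was not sized by power calculations. The primary safety objective is unaffected under every reading. How often this would happen cannot be judged from the documents.

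**What to change.** 1. In 6.4, limit the ban on PK samples to the affected dosing interval, or delete it. State that scheduled sampling resumes while the subject stays on dosing under 7.3.2.
2. In 6.4 and 7.3.1, replace the pointer to 5.3.3 with one to Section 7.3 and Appendix IV.
3. In Protocol 11.4.1 and SAP Section 9, define the affected treatment period as the affected Day 1 or Day 7 profile, so that a subject with one affected profile keeps the other in the PK analysis.

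The cost is wording in three protocol sections and one SAP section. No draws are added, because all are already scheduled. The downside is that a few samples may be assayed and then excluded.
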